2.5.2. Potential Benefits

TRC253 is an investigational product, and its efficacy has not been established. It is possible that the administration of TRC253 may result in clinical benefit (i.e., tumor response or prolonged stable disease).

2.6. Conduct

This clinical trial will be conducted in compliance with the protocol, GCP, and the applicable regulatory requirements.

3. TRIAL OBJECTIVES

3.1. Primary Objectives:

- Assess the safety of TRC253
- Determine the recommended Phase 2 dose (RP2D) of TRC253
- Evaluate prostate-specific antigen (PSA) response at Week 12 according to Prostate Cancer Working Group 3 (PCWG3) criteria ([Appendix 2](#))

3.2. Secondary Objectives:

- Evaluate exposure-QTcF relationship
- Determine the extent of receptor occupancy
- Evaluate the preliminary anti-tumor effects of TRC253

3.3. Exploratory Objective:

- Determine effect of treatment on resistance markers

4. TRIAL ENDPOINTS

4.1. Primary Endpoints

- Safety: adverse events, vital sign measurements, ECG parameters, physical examinations, and clinical laboratory tests
- RP2D of TRC253
- PSA response: serum PSA at Week 12 according to PCWG3 ([Appendix 2](#))

4.2. Secondary Endpoints

- PK parameters: maximum observed plasma concentration for each patient (C_{max}), observed plasma concentration at end of a dosing interval for each patient (C_{min}), time of maximum observed plasma concentration (t_{max}), area under the plasma concentration-time curve from time zero to 24 hours at steady state (AUC_{τ}), area under the plasma concentration-time curve from time zero to the last time measured (AUC_{last}), area under the plasma concentration-time curve from time zero extrapolated to infinite time (AUC_{∞}), apparent terminal elimination rate constant (λ_z), effective half-life ($t_{1/2eff}$), terminal half-life ($t_{1/2term}$), accumulation index (R_A), total apparent oral clearance (CL/F), and apparent oral volume of distribution at steady state (V_{ss}/F)
- Mean (90% confidence interval [CI]) change in QTcF at C_{max} and slope (90% CI)
- Time to PSA progression according to PCWG3 ([Appendix 2](#))
- Radiographic PFS (rPFS) according to PCWG3 ([Appendix 3](#))
- Central read of QTcF interval in part 2

4.3. Exploratory Endpoints

- Resistance markers assessed from circulating tumor cells (CTC) and circulating tumor DNA (ctDNA)
- Standard Uptake Value (SUV) of FDHT PET scan

5. STUDY DESIGN AND RATIONALE

5.1. Overview of Study Design

[figure not shown]
This is a multi-center, first-in-human, open-label, Phase 1/2A dose-escalation study in which eligible patients with metastatic CRPC will receive oral doses of TRC253. The study will be conducted in 2 parts as shown in [Figure 1](#).

5.1.1. Part 1 (Dose Escalation)

During Part 1 of the study, patients will be assigned sequentially to increasing TRC253 doses. The starting dose of TRC253 is 40 mg once daily in the morning, orally (see [Section 5.4](#) for starting dose justification). TRC253 doses will be escalated in subsequent cohorts after all patients enrolled in a given cohort have completed the 28-day DLT evaluation period. Dose escalation in Part 1 will follow single-patient dose escalation design until initial drug-related toxicity occurs per [Table 4](#). When an initial drug-related toxicity occurs per [Table 4](#) or DLT per [Table 6](#) in a single patient the cohort will be expanded according to 3+3 design rules. Cohorts may be expanded to include additional patients for purposes of collecting additional safety, PK, PD (FDHT-PET), and PSA response data. A single cohort may be expanded to a maximum of twelve patients to help inform selection of a MED, as long as that dose level remains below the MTD (see below).

[figure not shown]
Subsequent dose levels will enroll patients based on 3+3 design, whereby 3 patients will be initially enrolled and treated at each dose level. If one of these 3 patients experiences a dose-limiting toxicity (DLT) during the initial 28-day evaluation period, the dose level will be expanded to 6 patients. The MTD will have been exceeded if $\geq 33\%$ of patients experience DLT at a given dose level. DLT will have occurred when a patient has 1 or more toxicity listed in [Table 6](#) that is at least possibly related to TRC253 during the first 28 days of dosing. Patients who exit the study for reasons other than DLT prior to completion of the 28-day DLT evaluation period will be replaced to ensure an adequate safety assessment in each cohort. Patients who experience DLT who receive less than the prescribed dose of TRC253 due to documented toxicity during the DLT evaluation period will be considered evaluable for dose escalation purposes. At the MTD or MED, up to 12 patients may be enrolled.

Figure 4: Single Patient Dose Escalation Schematic

Abbreviations: DLT=dose-limiting toxicity, MTD=maximum tolerated dose.

Figure 5: 3+3 Dose Escalation Schematic

Abbreviations: DLT=dose-limiting toxicity, MTD=maximum tolerated dose.

Dosing during the study will occur as follows:

- The first cohort will receive the oral TRC253 starting dose of 40 mg daily.
- The proposed TRC253 doses are 40 mg, 80 mg, 160 mg, 240 mg, 320 mg, and 400 mg; however, intermediate dose levels may be implemented based on safety, tolerability, PK, PD and other observations at each dose level with consent of the medical monitor and Principal Investigators. Escalation to the next dose level will occur with consent of the medical monitor and treating Principal Investigators following review of safety, tolerability, PD and other observations at previous dose levels.
- Intra-patient dose escalation is allowed. A patient may dose escalate to a dose level at or below the maximum tolerated dose (MTD) if (1) the new dose level has been declared safe by the medical monitor and Principal Investigators, (2) the medical monitor has been consulted, (3) the disease has not progressed, and (4) the patient has completed three 28-day cycles of treatment at a given dose level (multiple dose escalations are permitted).

The MTD, maximum administered dose (MAD), minimum efficacious dose (MED), and RP2D are defined as follows:

- Maximum-tolerated Dose: MTD is the highest TRC253 dose at which the probability of DLT is < 33% (or < 2 out of 6).
- Maximum-administered Dose: MAD is the highest TRC253 dose administered in case the MTD cannot be defined.
- Minimum Efficacious Dose: MED is defined as the lowest TRC253 dose administered at which PK, mean plasma trough concentration (C_{trough}) > 335 ng/mL (623 nM) with demonstrable PD and efficacy data. In addition, data from FDHT-PET scans may be used to confirm the MED.
- Recommended Phase 2 Dose: RP2D will be equal to or below the MTD (or the MAD) and the MED. A lower dose of TRC253 may be selected as the RP2D on the basis of cumulative safety, PK, PD, and efficacy data.

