1. SYNOPSIS

Name of Sponsor/Company: TRACON Pharmaceuticals, Inc.	
Name of Investigational Product: TRC253	
Name of Active Ingredient: TRC253-HCl	
Title of Study: AN OPEN-LABEL PHASE 1/2A STUDY TO EVALUATE THE SAFETY, PHARMACOKINETICS, PHARMACODYNAMICS, AND PRELIMINARY EFFICACY OF TRC253, AN ANDROGEN RECEPTOR ANTAGONIST, IN PATIENTS WITH METASTATIC CASTRATION-RESISTANT PROSTATE CANCER	
Study center(s): 6 centers in Part 1, and approximately 20 centers in Part 2, in the United States	
Studied period: Date first patient enrolled: May 2017 Date of determination of recommended phase 2 dose (RP2D): July 2018 Estimated date last patient enrolled: April 2021 Estimated date last patient completed: October 2021	Phase of development: 1/2A
Rationale: TRC253 is a high-affinity, small molecule antagonist of the androgen receptor (AR) with inhibitory activity against wild type AR and specific mutated variants of AR. TRC253 blocks AR nuclear translocation as well as AR binding to DNA and is an antagonist of transcription for wild type AR and mutated AR. TRC253 is orally active and does not have agonist activity towards either the wild type or mutated ARs. TRC253 treatment in the Hershberger assay results in complete inhibition of androgen sensitive organ development. TRC253 is efficacious in an LNCaP xenograft model driven by F877L (previously known as F876L) mutant AR and inhibited other known AR resistance mutations, including L702H, in preclinical models.	
Objectives Primary Objectives: 
 Assess the safety of TRC253 Determine the recommended Phase 2 dose (RP2D) of TRC253 Evaluate prostate-specific antigen (PSA) response at Week 12 according to Prostate Cancer Working Group 3 (PCWG3) criteria (Appendix 2) Secondary Objectives: 
 Evaluate exposure-QTcF relationship Determine the extent of receptor occupancy Evaluate preliminary anti-tumor effects of TRC253 Exploratory Objective: 
 Determine effect of treatment on resistance markers 	
Endpoints Primary Endpoint:	

- Safety: adverse events, vital sign measurements, ECG, physical examinations, and clinical laboratory tests
- RP2D of TRC253
- PSA response: serum PSA at Week 12 according to PCWG3 ([Appendix 2](#))

Secondary Endpoints:

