In CYP induction and inhibition studies, TRC253 was not an inducer of human CYPs 1A2, 2B6, or 3A4 at concentrations up to 10 μ M (not assessed at 30 μ M due to cytotoxicity) and was not an inhibitor of CYPs 1A2, 2A6, 2C8, 2C9, 2D6, 2E1, or 3A4 at concentrations up to 100 μ M. TRC253 was a weak inhibitor of CYPs 2B6 and 2C19 (IC₅₀ values of 52 and 97 μ M, respectively); however, significant drug-drug interactions are not expected at the predicted maximum observed plasma concentration at steady state (C_{max,ss}; 206 ng/mL; 0.41 μ M to 2,688 ng/mL; 5.3 μ M) at the proposed clinical dose range 40 mg to 480 mg (highest proposed dose)/daily in this first-in-human study.

In drug efflux transporter studies, TRC253 was a substrate but not an inhibitor of multi-drug resistance protein 1, and was neither a substrate nor an inhibitor of breast cancer resistance protein.

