2.4. Phase 1 and Phase 2 253PC101 Ongoing Study Results

Twenty-two patients participated in the dose escalation portion of the study and initially enrolled at TRC253 doses of 40 (n=1), 80 (n=1), 160 (n=2), 240 (n=6), 280 (n=2), and 320 mg (n=10) and 12 have enrolled in the expansion portion. Although only 2 patients initially enrolled at 280 mg, 1 patient initially dosed at 240 mg dose escalated to 280 mg and 2 patients dosed at 320 mg dose reduced to 280 mg after the first dose; thus, a total of patients were evaluated at 280 mg prior to determination of the RP2D. There were no deaths, no drug-related serious adverse events (SAEs), and no grade 4 adverse events (AEs).

The maximum tolerated dose was not reached. However, the single DLT observed in the study of grade 3 QTcF prolongation occurred at the 320 mg dose level and steady state drug exposure at the 320 mg dose level significantly exceeded the target concentration. Therefore, dose escalation did not proceed to the 400 mg dose level and the 280 mg dose level was explored and declared the RP2D based on the lack of DLT and consistent steady state exposures above the target concentration. In general, TRC253 has been well-tolerated. Three patients discontinued due to AEs: 1 patient discontinued due to spinal cord compression secondary to disease progression, and 2 patients discontinued due to QTcF prolongation, both of which were suspected related to TRC253. Prolongation of QTcF of grade 1 or 2 severity has been seen in the majority of patients and requires serial monitoring of ECGs.

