5.4. Starting Dose Rationale

The TRC253 starting dose for this study is 40 mg once daily in the morning. This TRC253 starting dose is less than the safe starting dose according to Food and Drug Administration (FDA) guidelines for oncology agents in cancer patients, using nonclinical safety data.

The selection of the TRC253 starting dose is supported by toxicology results obtained in the rat as the most sensitive species. In the rat, the severely toxic TRC253 dose in 10% of the rats (STD10) was determined to be 100 mg/kg. The human equivalent dose (HED) was calculated by normalization of the TRC253 dose to the body surface area. A default safety factor of 10 was applied to provide a margin of safety for protection of human patients relative to STD10 and a TRC253 dose of 60 mg/m² was determined. In consequence, for a human with a surface area of 1.8 m², the highest potential starting dose was calculated to be 108 mg.

However, the final selection of the starting dose was ultimately based on the potential pharmacologic activity of TRC253. Pharmacologic efficacy parameters were obtained from the LNCaP F877L mouse xenograft model and the Hershberger assay that assessed the effect of TRC253 on androgen dependent organ development) to estimate the potential efficacious TRC253 concentration and plasma exposure in humans. Applying these parameters, a TRC253 starting dose of 65 mg once daily was projected to achieve the median target human exposure (335 ng/mL) over the 24 hr dosing interval. A dose of 40 mg per day was therefore selected to provide for a starting dose expected to be safe without causing complete AR receptor occupancy.

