14. STATISTICAL METHODS

Statistical analysis will be done by the sponsor or under the authority of the sponsor. A general description of the statistical methods to be used to analyze the efficacy and safety data is outlined below. Specific details will be provided in the Statistical Analysis Plan.

No formal hypothesis testing will be conducted. Data will be summarized using descriptive statistics. Continuous variables will be summarized using the number of observations, mean, standard deviation, coefficient of variation, median, and range as appropriate. Categorical values will be summarized using the number of observations and percentages as appropriate. Time-to-event endpoints will be summarized using Kaplan-Meier estimates.

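### The MED trough threshold is printed as 335 ng/mL and as 623 nM, but on the conversions in Section 2.2.3 these are different concentrations, about 6 to 7% apart

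*Combined protocol and SAP*

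**What the plan says.** Section 5.1.1 defines the MED as the lowest dose with a mean trough "> 335 ng/mL (623 nM) with demonstrable PD and efficacy data", and refers to the MED again when it defines the RP2D. Section 5.4 gives the same target in mass units only: a dose was "projected to achieve the median target human exposure (335 ng/mL) over the 24 hr dosing interval". Section 2.4 rests the choice of 280 mg on the absence of DLT and on "consistent steady state exposures above the target concentration", without trough values in that paragraph.

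The protocol also converts TRC253 concentrations in Section 2.2.3, where the predicted maximum steady-state concentration is given as "206 ng/mL; 0.41 μ M to 2,688 ng/mL; 5.3 μ M) at the proposed clinical dose range 40 mg to 480 mg (highest proposed dose)/daily". The Synopsis names the product as a salt ("Name of Active Ingredient: TRC253-HCl"). The text reviewed gives no molecular weight and does not say whether plasma concentrations, or the threshold, are expressed as salt or as free base.

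**The concern.** A threshold printed in two units is one threshold only if the conversion is right. If it is not, a mean trough lying between the two readings meets the MED in one unit and misses it in the other. The figure is a decision rule and not background: it defines the MED, the MED enters the RP2D definition, and the RP2D is a primary endpoint (Section 4.1). Sections 8.4 and 8.5 still refer to the MED when they describe dose moves and Part 2 dosing.

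**Working it through.** **Inputs.** Three mass and molar pairs: one from Section 5.1.1 and two from Section 2.2.3 ("206 ng/mL; 0.41 μ M to 2,688 ng/mL; 5.3 μ M"). Each printed figure is taken as rounded to its last digit, so it may be off by half a unit in that digit.

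**Step 1: implied molecular weight.** Formula: weight (g/mol) = 1000 × (ng/mL) / (nM).

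| Source | Calculation | g/mol | Range with rounding |
|---|---|---|---|
| 5.1.1 | 1000 × 335/623 | 537.7 | 334.5/623.5 to 335.5/622.5: 536.5 to 539.0 |
| 2.2.3, low end | 1000 × 206/410 | 502.4 | 205.5/415 to 206.5/405: 495.2 to 509.9 |
| 2.2.3, high end | 1000 × 2,688/5,300 | 507.2 | 2,687.5/5,350 to 2,688.5/5,250: 502.3 to 512.1 |

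The two pairs in Section 2.2.3 agree with each other; weights compatible with both run from 502.3 to 509.9. The Section 5.1.1 range overlaps neither pair, so rounding does not explain the difference.

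**Step 2: try to reproduce 623 nM.** With the Section 2.2.3 weights:
- 1000 × 335/502.4 = 667 nM and 1000 × 335/507.2 = 661 nM. Over the full common range: 1000 × 335/509.9 = 657 to 1000 × 335/502.3 = 667 nM.
- In reverse, 623 × 502.3/1000 = 313 to 623 × 509.9/1000 = 318 ng/mL.

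The printed 623 nM is not reproduced.

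**Step 3: try the other direction.** At 537.7 g/mol, 206 ng/mL would be 206/537.7 = 0.38 μM and 2,688 ng/mL would be 2,688/537.7 = 5.0 μM. Section 2.2.3 prints 0.41 and 5.3.

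**Step 4: size of the gap.**
- At the printed figures: 537.7/507.2 − 1 = 6.0%; 537.7/502.4 − 1 = 7.0%.
- With all rounding: 536.49/509.88 − 1 = 5.2%; 538.96/502.34 − 1 = 7.3%.

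**Step 5: could one conversion use the salt and the other the free base?** The weight of HCl is not in the documents; 36.46 g/mol is assumed here. Subtracting it from the Section 5.1.1 range gives 536.49 − 36.46 = 500.0 to 538.96 − 36.46 = 502.5. This meets the Section 2.2.3 range only between 502.3 and 502.5. The explanation is possible but fits only at the edge.

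**The case against.** The strongest reply is that there is in practice one threshold. The rule in Section 5.1.1 leads with 335 ng/mL, the molar value is a parenthesis, and Section 5.4 repeats 335 ng/mL alone. That makes 335 ng/mL the better supported figure. It does not prove the molar value wrong: the text shows no source calculation, and the error could instead lie in Section 2.2.3.

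The second reply is that the error runs in one direction. The alternative mass reading is lower (313 to 318 ng/mL), so any mean trough above 335 ng/mL also exceeds 623 nM. This stands. A reader might infer that the 280 mg RP2D is in doubt. The documents do not support that: Section 2.4 reports exposures above target at that dose, nothing says the comparison was made in nM, and the choice also rested on the absence of DLT. The MED itself requires PD and efficacy data as well as the trough.

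Two further inferences are tempting and unsupported. One is that salt and free base were confused, so that every stated dose is off by the same factor; nothing in the text ties capsule strength to either basis. The other is that comparisons with the potencies in Table 3 are upset. That table is already in molar units, the protocol does not convert the threshold for comparison with it, and its values run from 0.0069 to 16.8 μM, a span against which 6 to 7% changes nothing.

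Finally, Section 2.4.3 (Phase 1 pharmacokinetics) was not in the text reviewed, and Section 2 defers detail to the Investigator's Brochure. Trough values or the assay basis may be given there, so their absence here is not counted against the plan.

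**Conclusion.** The inconsistency is real and exceeds rounding. Sections 5.1.1 and 2.2.3 cannot both be right on one molecular weight; the gap is 6.0 to 7.0% at the printed figures and 5.2 to 7.3% at the rounding limits. Which figure is wrong is not settled.

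The consequence is narrow. It matters only for a dose level whose mean trough lies between about 313 and 335 ng/mL, and whether any does cannot be judged from the text reviewed. The finding does not by itself undermine the RP2D. That conclusion assumes that the target in Section 2.4 is the 335 ng/mL of Sections 5.1.1 and 5.4, and that measured troughs and threshold share one mass basis. As "No formal hypothesis testing will be conducted", no error rate or power figure is affected. A mix of salt and free-base weights is one possible cause, not an established one.

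**What to change.** Reconcile Sections 2.2.3, 5.1.1 and 5.4 as follows:
- State one molecular weight and one basis (salt or free base) for the threshold and the plasma assay.
- Correct whichever of the printed figures does not follow from the source calculation.
- Say in which single unit the threshold is applied.
- When reporting the MED, re-check the existing mean troughs by dose level against the reconciled threshold.

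The cost is a corrected figure or two and one re-check of data already collected. The downside is that the stated margin over target may shift by about 5 to 7%.

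Separately, the same sentence of Section 2.2.3 calls 480 mg the highest proposed dose, whereas the Synopsis and Sections 5.1.1 and 8.5 end the proposed list at 400 mg. These passages must also be reconciled; the point has no bearing on the threshold.

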5.1.2. Part 2 (Dose Expansion)

[figure not shown]
Part 2 will consist of three cohorts of initially up to 15 patients (Cohort 1), up to 30 patients (Cohort 2), and up to 15 patients (Cohort 3) to receive TRC253 at the RP2D of 280 mg. The objective of Part 2 is to gather additional information on the safety, PK and PD characteristics, and the clinical efficacy of TRC253 in a pre-defined population of patients with metastatic CRPC. Patients enrolled into Part 2 will have received prior treatment with enzalutamide or apalutamide. Patients will be centrally screened for the presence of the AR F877L and AR L702H mutations from a plasma sample and enrolled into Cohort 1 (AR F877L positive), Cohort 2 (patients without AR F877L and without sole AR L702H mutations), or Cohort 3 (sole AR L702H mutation positive). Note that Cohort 1 patients may be positive for F877L alone or F877L associated with any other AR mutation.

Cohort 1: metastatic CRPC patients with prior enzalutamide or apalutamide and with evidence of AR F877L mutation will be enrolled at the RP2D of 280 mg (AR F877L mutation positive). Note that Cohort 1 patients may be positive for F877L alone or F877L associated with any other AR mutation.

Cohort 2: metastatic CRPC patients with prior enzalutamide or apalutamide without evidence of AR F877L and sole AR L702H mutations but with a different AR mutation or any other mechanism of acquired resistance will be enrolled at the RP2D of 280 mg (AR F877L and sole AR L702H mutation negative).

Cohort 3: metastatic CRPC patients with prior enzalutamide or apalutamide and with evidence of AR L702H mutation will be enrolled at the RP2D of 280 mg (sole AR L702H mutation positive).

Figure 6: Part 2 Cohorts

5.2. Dose-Limiting Toxicity

Toxicities will be graded for severity according to the National Cancer Institute Common Terminology Criteria for Adverse Events (NCI-CTCAE), Version 4.03.

The DLT evaluation period is 28 days starting from the Cycle 2 Day 1 dose of TRC253 in Part 1 due to the anticipated long half-life.

Only patients who have received $\geq 75\%$ of TRC253 doses during the DLT evaluation period will be considered evaluable. Patients who have received $\leq 75\%$ of TRC253 doses during the DLT evaluation period due to reasons other than toxicities, such as but not restricted to disease progression, missed appointments, non-compliance, and patient withdrawal, will be considered non-evaluable for DLT and will be replaced with a new patient.

Table 4: Single Patient Dose Escalation

Dose Escalation Will Proceed in the Absence of the Following Toxicities:	
Toxicity Category	Drug-Related Toxicity and Grade
Hematologic	Grade \geq 3 neutropenia for > 5 days
	Grade 3 febrile neutropenia
	Grade 3 thrombocytopenia
Non-hematologic	Grade \geq 2 non-hematological toxicity, with the following exceptions: 
 • Grade 2 nausea, vomiting, or diarrhea responsive to symptomatic treatment • Grade 2 fatigue in a patient with Grade 1 fatigue at baseline • Transient grade 2 laboratory abnormality that the investigator does not believe is clinically significant
	Grade \geq 2 QTcF prolongation or increase in QTcF of > 30 ms from baseline
	Missing > 7 days doses for toxicity in Cycle 2

Table 5: Decision Rules for 3+3 Dose Escalation

Number of patients with DLT in a given dose cohort	Escalation Decision Rules
0 out of 3	Proceed to the next dose cohort.
1 out of 3	Enter more patients up to a total of 6 patients into this dose cohort.
1 out of 6	Proceed to the next dose cohort.
>1 out of 3	Stop dose escalation. Declare this dose cohort as the DLT dose level. Enroll additional patients up to a total of 6 patients into the next lower dose cohort, if <6 patients were treated previously.
\geq 2 out of 6	Stop dose escalation. Declare this dose cohort as the DLT dose level. Enroll additional patients up to a total of 6 patients into the next lower dose cohort, if <6 patients were treated previously.

Table 6: 3+3 Dose Escalation DLT Definition and Criteria

Toxicity Category	Drug-Related Toxicity and Grade
Hematologic	Grade 4 neutropenia for > 5 days
	Grade 3 febrile neutropenia
	Grade 3 thrombocytopenia with hemorrhage or Grade 4 thrombocytopenia
Non-hematologic	Grade \geq 3 non-hematological toxicity, with the following exceptions: 
 • Grade 3 nausea, vomiting, or diarrhea lasting < 72 hours in the absence of maximal medical therapy • Grade 3 fatigue < 5 days
	Grade \geq 3 QTcF prolongation or increase in QTcF of > 60 ms from baseline

	Missing > 7 days doses for toxicity in Cycle 2
	Grade \geq 1 seizure

